4.3.3 Corneal Fluorescein Staining (CFS) including Complete Corneal Clearing

CFS will be used to assess corneal damage and will be measured at each scheduled visit and at the premature study discontinuation visit. It will be graded using the modified Oxford scale, which is a 7-point ordinal scale in which a score of 0 represents no staining dot, and scores of 0.5, 1, 2, 3, 4, or 5 represent increased numbers of staining dots, corresponding to increased severity of corneal damage. A CFS grade of 0 represents complete corneal clearing.

A decrease from baseline in CFS indicates improvement.

4.3.4 Higher-Order Aberrations (HOA)

At the Screening Visit and Month 3/premature study discontinuation visit, serial measurements of ocular higher-order aberrations (HOA) are performed by means of the Hartmann-Shack wavefront aberrometer. HOA will be measured during a blink-free period of 20 seconds without instillation of topical anaesthesia. Because HOA data will not be collected at the Baseline Visit (Day 1), data collected from the Screening Visit will be used as the baseline measures in change from baseline analyses.

The following HOA parameters will be collected:

- **Root mean square (RMS)**: RMS is calculated from the Zernike coefficients to represent the wavefront aberrations. A decrease from baseline in RMS indicates improvement.
- **Coma-like aberrations (S3)**: S3 is the RMS of the third-order Zernike coefficients.
- Spherical-like aberrations (S4): S4 is the RMS of the fourth-order Zernike coefficients.
- Total higher-order aberrations (S3 + S4): S3 + S4 is the sum of the third-order and fourth-order Zernike coefficients.

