# 5.2.2 Secondary Endpoints

# 5.2.2.1 Efficacy Endpoints

- CFS score assessed with the Modified Oxford Scale and change from baseline at Months 1, 2 and 3.
- FVA parameters (starting visual acuity, FVA, LogMAR FVA, visual maintenance ratio (VMR), and maximal and minimal visual acuities) and their change from baseline at Months 1, 2 and 3.
- OSI and its variance and their change from baseline at Months 1, 2 and 3.
- Correlation between CFS changes over time and OSI changes over time and other FVA parameters changes over time, separately.
- Correlation between each OSI parameters changes overtime and FVA parameters changes overtime, separately.
- Root mean square (RMS) of higher order aberrations (total, coma-like, spherical like) measured with Hartmann-Schack aberrometer and their change from baseline at Month 3.
- Tear Break Up Time (TBUT) and change from baseline at Months 1, 2 and 3.
- Patient Global Evaluation of Efficacy at Month 3.
- VAS scores (photophobia, blurred vision) and their change from baseline at Months 1, 2 and 3.
- Investigator Global Evaluation of Efficacy at Month 3.
- Artificial Tear use and change from baseline at Months 1, 2 and 3.

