## Appendix A-VI Higher Order Aberrations

Serial measurements of ocular higher-order aberrations are performed by means of Hartmann-Shack wavefront aberrometer.

Higher-order aberrations will be measured during a blink-free period of 20 seconds without instillation of topical anesthesia.

The higher-order aberration data will be analysed quantitatively for the central 4-mm-diameter zone up to the fourth order by expanding the set of Zernike polynomials. From the Zernike coefficients, the root mean square (RMS) will be calculated to represent the wavefront aberrations. The third-order Zernike coefficients (coma-like aberrations, S3), fourth-order Zernike coefficients (spherical-like aberrations, S4), and total higher-order aberrations (S3 + S4) will be calculated.

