2.2.2 Secondary Endpoints

2.2.2.1 Efficacy Endpoints

- CFS score assessed with the Modified Oxford Scale and change from baseline at Months 1, 2 and 3.
- FVA parameters (LogMAR FVA, VMR, starting LogMAR VA, minimal LogMAR VA, and maximal LogMAR VA) and their change from baseline at Months 1, 2 and 3.
- OSI and its variance and their change from baseline at Months 1, 2 and 3.
- Correlation between CFS changes over time and OSI changes over time and other FVA parameters changes over time, separately.
- Correlation between each OSI parameters changes over time and FVA parameters changes over time, separately.
- Root mean square (RMS) of higher order aberrations (total, coma-like, spherical-like) measured with Hartmann-Schack aberrometer and their change from baseline at Month 3.
- Tear Break Up Time (TBUT) and change from baseline at Months 1, 2 and 3.
- Patient Global Evaluation of Efficacy at Month 3.
- VAS scores (photophobia, blurred vision) and their change from baseline at Months 1, 2 and 3.
- Investigator Global Evaluation of Efficacy at Month 3.
- Artificial Tear use and change from baseline at Months 1, 2 and 3.

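### SAP 4.3.4 defines total higher-order aberration as a sum of Zernike coefficients, which is not the RMS named as the secondary endpoint

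*SAP*

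**What the plan says.** The endpoint is an RMS for all three components. Protocol 5.2.2.1 has "Root mean square (RMS) of higher order aberrations (total, coma-like, spherical like"; SAP 2.2.2.1 has "Root mean square (RMS) of higher order aberrations (total, coma-like, spherical-like". In both, the change is assessed at Month 3.

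SAP 4.3.4 opens its list of variables with "The following HOA parameters will be collected" and gives four items:

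- a general RMS item: "RMS is calculated from the Zernike coefficients to represent the wavefront aberrations". It states neither which orders are included nor that it is the total;
- coma-like: "S3 is the RMS of the third-order Zernike coefficients";
- spherical-like: "S4 is the RMS of the fourth-order Zernike coefficients";
- total: "S3 + S4 is the sum of the third-order and fourth-order Zernike coefficients".

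The last item is the SAP's only definition of the total. Protocol Appendix A-VI says "From the Zernike coefficients, the root mean square (RMS) will be calculated to represent the wavefront aberrations", limits the analysis to a 4-mm zone up to the fourth order, and labels the total S3 + S4 without saying how the two combine.

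SAP 8.2.1 summarises the endpoint descriptively, including a coefficient of variation. SAP 8.2.3.1 correlates change in HOA RMS with change in CFS and with change in LogMAR FVA, without saying which component is meant. SAP section 10, which lists changes from the protocol, does not mention the definition of the total.

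**The concern.** The definition of the total does not describe the endpoint. It contains no squaring and no square root, and it does not match its own label: S3 and S4 have just been defined as RMS values, so S3 + S4 would be a sum of two RMS values and not of coefficients.

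A contract research organisation analyses the data from the SAP, so a programmer could act on this wording. Under the literal reading, positive and negative coefficients offset each other, and a markedly aberrated eye can have a total near zero or below it. A coefficient of variation, which protocol section 12.4 wants for planning a further study, is unstable for a quantity whose mean may lie near zero. Under the label reading, the total is positive but too large. In either case the HOA RMS correlations in SAP 8.2.3.1 do not identify the variable they use.

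**Working it through.** The documents give no aberration values, so there is no figure of the plan's own to reproduce. The check compares three readings of the total. All coefficient values below are assumed for illustration.

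**Readings**

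- A, SAP wording: the sum of all third- and fourth-order coefficients, with their signs.
- B, the label: S3 + S4, each already an RMS.
- C, the endpoint: the RMS over both orders, sqrt(S3² + S4²), where S3 and S4 are each the square root of a sum of squared coefficients.

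**Worked example**

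Assumed third-order coefficients: 0.10, −0.15, 0.08, −0.05. Assumed fourth-order coefficients: 0.03, −0.02, 0.12, −0.04, 0.02.

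- S3² = 0.0100 + 0.0225 + 0.0064 + 0.0025 = 0.0414, so S3 = 0.203.
- S4² = 0.0009 + 0.0004 + 0.0144 + 0.0016 + 0.0004 = 0.0177, so S4 = 0.133.
- Reading C: sqrt(0.0414 + 0.0177) = sqrt(0.0591) = 0.243.
- Reading B: 0.203 + 0.133 = 0.337 before rounding of the parts.
- Reading A: −0.02 + 0.11 = 0.090.

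**Reading B against C in general**

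With r = S4/S3, the ratio is (S3 + S4)/sqrt(S3² + S4²) = (1 + r)/sqrt(1 + r²). This is algebra; only the S3/S4 pairs are assumed.

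- 0.30/0.05: 0.35/sqrt(0.0925) = 1.15, or 15% too large.
- 0.20/0.10: 0.30/sqrt(0.0500) = 1.34, or 34% too large.
- S3 = S4: 2/sqrt(2) = 1.41, or 41% too large, the maximum.

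**Ranks**

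The SAP's association analyses of HOA RMS use Spearman's coefficient, so ranks matter more than levels there. In 200,000 simulated eyes with nine independent zero-mean coefficients (SD 0.1, assumed), the Spearman correlation of reading B with reading C was 0.987 for values. It was 0.999 for changes when all coefficients of an eye were scaled by one common factor. For reading A against C it was 0.00, and A was negative in about 50% of eyes.

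**Dependence on convention**

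The formula sqrt(S3² + S4²) holds only if each S is a root *sum* of squares. If RMS is taken literally as a root *mean* of squares over 4 and 5 coefficients, the example gives S3² = 0.0414/4 = 0.01035 and S4² = 0.0177/5 = 0.00354. The root mean over all nine is sqrt(0.0591/9) = 0.081, whereas sqrt(0.01035 + 0.00354) = 0.118. The documents do not state which convention applies.

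**The case against.** The strongest reply is that the item describes a collected variable and is not a formula to be run. SAP 4.3.4 lists these quantities as collected, does not list individual coefficients, and gives no derivation step; Appendix B has no code for them. If the aberrometer exports a total RMS and that number was recorded, the analysed value is right and only the description is faulty. This stands as a real possibility. Appendix A-VI says the quantities will be calculated but not by whom, so the documents do not settle it.

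It can also be said that the endpoint wording and SAP 8.2.1 call the total an RMS, which makes a signed sum the least plausible intention, and that the general RMS item may be the total. Both are fair, but the SAP does not say so, and the one sentence that defines the total says something else.

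A reader might infer from the simulation that the trial's total is unrelated to true aberration, or negative in half of eyes. The documents do not support that. The 0.00 and 50% follow directly from assuming independent zero-mean coefficients and say nothing about these patients. A reader might also infer that the SAP applies its improvement rule to a signed sum. It does not: SAP 4.3.4 and protocol 9.3.4.4 attach the rule that a decrease is improvement to RMS. The rule would lose its meaning only if the signed sum were analysed in place of an RMS.

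**Conclusion.** The definition of the total in SAP 4.3.4 is inconsistent with the named endpoint and should be corrected. Neither literal reading yields the RMS of total higher-order aberration. The signed sum is a different quantity, while S3 + S4 overstates the level by 15% to 41% over the assumed pairs and leaves Spearman ranks almost unchanged under the simulated conditions.

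It would go too far to conclude that the trial's reported total is wrong. That depends on what was recorded and programmed, which the documents leave open. The reach is limited to one secondary endpoint, summarised descriptively in an exploratory study that enrolled 17 patients, and possibly to the HOA RMS correlations added in the SAP. The two primary correlations, of CFS change with change in VMR and with change in variance of OSI, do not use this variable.

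**What to change.** In SAP 4.3.4, replace the definition of the total with one of these:

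- total HOA RMS is the square root of the sum of squared third- and fourth-order coefficients over the 4-mm zone, which equals sqrt(S3² + S4²) when S3 and S4 are each a root sum of squares; state that convention explicitly; or
- total HOA RMS is the total RMS up to fourth order as reported by the aberrometer.

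Name that quantity as the total in SAP 8.2.1 and as HOA RMS in 8.2.3.1, and align protocol Appendix A-VI. Before programming, confirm which number was entered on the eCRF. If only S3 and S4 were recorded as root sums of squares, the total can be computed from them. The cost is one formula and two cross-references, with no new data.

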4.3.5 Symptoms Measured on Visual Analogue Scales (VAS)

Patient's photophobia and blurred vision will be assessed on each eye, separately, at each scheduled visit and at the premature study discontinuation visit using a visual analogue scale (VAS). The VAS ranges from 0% to 100%; 0% corresponds to "no discomfort" and 100% corresponds to "maximal discomfort".

A decrease from baseline in the VAS indicates improvement.

4.3.6 Tear Break-Up Time (TBUT)

Tear break-up time (TBUT) will be measured by determining the time to tear break-up at each scheduled visit and at the premature study discontinuation visit. At each visit, the TBUT will be measured twice. If the 2 readings differ by more than 2 seconds, a third reading will be taken. This measurement will be performed with 10 seconds maximum. The TBUT value will be the average of the 2 or 3 measurements. A measured value of less than 10 seconds will be recorded; a measured value of 10 seconds or greater will be recorded as 10 seconds.

An increase from baseline in TBUT indicates improvement.

4.3.7 Schirmer Test (without Anaesthesia)

At the Baseline Visit (Day 1) and Month 3/premature study discontinuation visit, Schirmer test will be performed without anaesthesia to record the length of the tear absorption on the strip in 5 minutes. It will be recorded as mm wetting/5 min.

An increase from baseline in Schirmer test indicates improvement.

4.3.8 Patient Global Evaluation of Efficacy

At the Month 3/premature study discontinuation visit, patients will provide an overall assessment of the effect of the study medication using the following rating scale:

- (3) = Very satisfactory
- (2) = Satisfactory
- (1) = Not very satisfactory
- (0) =Unsatisfactory.

4.3.9 Investigator Global Evaluation of Efficacy

At the Month 3/premature study discontinuation visit, the study investigator will provide an overall assessment of the effect of the study medication on the improvement of that patient's DED using the following rating scale:

- (3) = Very satisfactory
- (2) =Satisfactory
- (1) = Not very satisfactory
- (0) = Unsatisfactory.

4.3.10 Use of Concomitant Artificial Tears

The use of artificial tears (AT) will be monitored over the course of the study for each patient. At each scheduled visit and at the premature study discontinuation visit, patients will be asked about the average number of times per day artificial tears were used the week preceding the visits, and

the number of days they were not used during the week preceding the visits. Patients will be allowed to instill 1 unpreserved artificial tear drop, up to eight instillations per day in each eye, to ameliorate their dry eye symptoms. Artificial tear usage in the past 7 days will be derived using the following equation:

AT usage = Average number of times per day used $AT \times (7 - number of days without AT use)$

A decrease from baseline in the AT usage indicates improvement.

4.4 Safety-Related Definitions

4.4.1 Adverse Event (AE)

Events reported on the AE electronic case report form (eCRF) will be assessed according to the amended FDA regulations 21 CFR Parts 312 and 320.

Under Protocol NVG16E128, an AE is defined as any untoward medical occurrence in a clinical investigation patient administered an investigational product; it does not necessarily have to have a causal relationship with the treatment. An AE will be considered as a *pre-treatment event* (PTE) if the AE occurred after the patient has signed informed consent to participate in the study but prior to administration of any study medication; it does not necessarily have to have a causal relationship with study participation. An AE will be considered as *treatment-emergent* if the AE occurred on or after the treatment start date up to the last study visit or worsened relative to pre-treatment state.

The severity of each AE will be graded by the Clinical Investigator as Mild (aware or unaware of event, but easily tolerated), Moderate (discomfort enough to cause interference with usual activity), or Severe (incapacitating; unable to work or perform usual activity). AEs will also be rated by the Investigator as to their causality/relationship to the study medication, to the Sponsor provided artificial tears, as well as to the study procedures (related vs. not related).

Each AE will be classified into a system organ classification (SOC) and coded to a preferred term (PT) using Medical Dictionary for Regulatory Activities (MedDRA, version v19.1 English, March 2016).

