## 8.1.4 Dose and Regimen

During the 3-month study unpreserved artificial tears and the study medication must be dispensed only to study patients in accordance with the study protocol:

• At the Screening Visit each patient will be dispensed unpreserved artificial tears for use during the 2-week wash-out phase.

• At the Baseline Visit (on Day 1), after the validation of all inclusion and exclusion criteria, each eligible patient will be given unpreserved artificial tears and one sealed cardboard box containing enough study medication for the period Day 1 - Month 1.

• At Month 1 Visit, each patient will be given unpreserved artificial tears and one sealed cardboard box containing enough treatment for the period Month 1 - Month 2.
IKERVIS®	
Study NVG16E128	Page 36 of 93
Protocol Version 4.0	23 March 2018

• At Month 2 Visit, each patient will be given unpreserved artificial tears and another sealed cardboard box containing enough treatment for the period Month 2 – Month 3.

At Screening Visit, each patient will be instructed to instil with unpreserved artificial tears up to eight times per day in each eye for the relief of their symptoms of DED, during the 3-month study treatment period. At the following visits, their compliance will be checked, and they will be instructed to pursue the use of unpreserved artificial tears according to their DED symptoms within the protocol limits.

At Baseline Visit (Day 1), each patient will be instructed to instil one drop of study medication (IKERVIS®, 1mg/ml ciclosporin) into the lower conjunctival sac of each eye once daily at bedtime during the 3-month study treatment period. Each single-unit container of study medication yields two drops of study medication (one drop for instillation in each eye) and will be used only once. At the following visits, their compliance will be checked, and they will be instructed to pursue the treatment with IKERVIS® with the same regimen.

Changes in the IKERVIS® regimen during the study are not permitted.

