## 9.2 Monitoring Patient Treatment Compliance

Study medication will be administered on Day 1, Month 2 and Month 3. The date and time of each dose will be recorded in the source documents and on the eCRF. An inventory of the study medication supplies dispensed will be performed by the site pharmacist or authorized study designee and recorded onto the Drug Accountability Log in the patient's source document records or equivalent. If a patient is persistently noncompliant with the study medication, the patient might be withdrawn from the study. All patients should be reinstructed about the dosing requirement during study visits. The authorized study personnel conducting the re-education must document the process in the patient source records.

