#### 10.2.1.2 PTE and AE Reporting

At each study visit, the investigator will assess whether any AEs have occurred. A neutral question, such as "How have you been feeling since your last visit?" may be asked. Patients may report AEs occurring at any other time during the study. Patients experiencing a serious PTE must be monitored until the symptoms subside and any clinically relevant changes in laboratory

IKERVIS®	
Study NVG16E128	Page 56 of 93
Protocol Version 4.0	23 March 2018

values have returned to Baseline or there is a satisfactory explanation for the change. Nonserious PTEs, related or not related to the study procedure, need not to be followed-up for the purposes of the protocol.

All patients experiencing AEs, whether considered associated with the use of the study medication or not, must be monitored until the symptoms subside and any clinically relevant changes in laboratory values have returned to Baseline or until there is a satisfactory explanation for the changes observed. All PTEs and AEs will be documented in the PTE/AE page of the eCRF, whether or not the investigator concludes that the event is related to the drug treatment. The following information will be documented for each event:

- Event term.
- Start and stop date and time.
- Severity.
- Investigator's opinion of the causal relationship between the event and administration of study medication(s) (Related or Not related) (not completed for PTEs).
- Investigator's opinion of the causal relationship to study procedure(s), including the details of the suspected procedure.
- Action concerning study medication (not applicable for PTEs).
- Outcome of event.
- Seriousness.

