## 12.6 AEs

Adverse events will be coded using the MedDRA dictionary. Frequencies and percentages will be provided of patients with treatment-emergent adverse events (TEAEs), serious TEAEs, and TEAEs causing premature discontinuation. An adverse event is treatment emergent if it occurs or worsens after the first dose of study treatment. Furthermore, frequencies will be given of patients with TEAEs as follows: 1) by system organ class, by system organ class and preferred term, 2) by system organ class, preferred term and maximal severity, 3) by system organ class, preferred term and strongest relationship, and 4) by system organ class, preferred term, maximal severity, and strongest relationship.

Separate analyses will be performed for ocular and systemic adverse events. Ocular AEs will be summarised for the analysis eye and the other eye separately.

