4.1.2 Baseline Visit (Day 1)

The *Baseline Visit* is the Day 1 visit when the subject will receive the first dose of the study medication.

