4.1.3 Analysis Period and Treatment Start and End Dates

There will be only one analysis period for this study:

Analysis Period	Analysis Period Start Date	Analysis Period End Date	
Open-label treatment period	The date of the first dose of the study medication administration	The Study Exit date	

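### The SAP dates treatment-emergent events from the calendar day of the first dose, so a Day 1 event before the bedtime dose is both pre-treatment and treatment-emergent

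*SAP*

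**What the plan says.** SAP 4.4.1 gives both definitions in one paragraph. A PTE arises after consent "but prior to administration of any study medication". A TEAE is an event that "occurred on or after the treatment start date up to the last study visit", or one that worsened from its pre-treatment state. SAP 4.1.3 starts the treatment period at "The date of the first dose of the study medication administration", and SAP 4.1.2 describes Baseline as the "Day 1 visit when the subject will receive the first dose of the study medication".

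Protocol 8.1.4 has the patient instil one drop into the lower conjunctival sac "of each eye once daily at bedtime during the 3-month study treatment period", and SAP 3.1 also gives bedtime. Protocol 9.1.3 puts assessments before study drug unless otherwise indicated.

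Protocol 12.6 uses the dose, not the date: "An adverse event is treatment emergent if it occurs or worsens after the first dose of study treatment". Protocol 10.2.1.1 ends PTE collection and begins AE collection when study medication is first administered. SAP 9.1 summarises PTEs and TEAEs separately and has no tie-break for Day 1.

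**The concern.** The two SAP definitions run on different clocks: one on a moment, the other on a calendar date. Between the start of Day 1 and the bedtime dose, both can be true of the same event.

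That interval contains the Baseline visit. Protocol 9.3.2.1 schedules tear break-up time and corneal staining (both with fluorescein), dilated fundus examination, tonometry and the Schirmer test. Protocol 4.3 names possible allergy to fluorescein and to anaesthetic drops, and irritation from the Schirmer test, among the risks of taking part. An event at that visit, before any exposure to the drug, is therefore foreseeable.

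Ocular tolerability is a secondary objective and there is no control arm, so the TEAE tables carry the tolerability description. An event that precedes all exposure does not belong in them, and should not also appear in the PTE tables.

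There is a practical mismatch too. Protocol 10.2.1.2 says drug causality is not completed for PTEs. A Day 1 pre-dose event that the site correctly enters as a PTE would reach the SAP's TEAE tables without a drug-relationship value, although SAP 9.1 tabulates events by relationship.

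**Working it through.** The plan gives no figure to reproduce. The check applies each definition to one test event.

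**Test event:** onset on Day 1 during the clinic visit, after consent; first dose at bedtime the same day; no later worsening.

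| Rule | Condition | Result |
|---|---|---|
| PTE, SAP 4.4.1 | after consent, before first administration | met |
| TEAE, SAP 4.4.1 | onset date on or after treatment start date | met (dates are equal) |
| TEAE, protocol 12.6 | onset or worsening after the first dose | not met |
| PTE, protocol 10.2.1.1 | between consent and first administration | met |

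The event is in both categories under the SAP, and is a PTE only under the protocol.

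**Does this depend on when the first dose is taken?**
- Bedtime on Day 1 (protocol 8.1.4, SAP 3.1): overlap, as above.
- At the Day 1 visit (a possible reading of SAP 4.1.2 and protocol 9.2): overlap remains for events during the assessments, because protocol 9.1.3 puts those before study drug.
- On a later date: no overlap, because the Day 1 visit then precedes the treatment start date. SAP 4.1.2 does not foresee this.

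**Can another SAP rule resolve it?** SAP 6.2.3 imputes partial dates, not times. SAP 4.1.4 counts in whole days. SAP 9.1 says nothing on precedence.

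**Are the times available?** Protocol 10.2.1.2 requires "Start and stop date and time" for each event. Protocol 9.2 says "The date and time of each dose will be recorded in the source documents and on the eCRF". However, the sentence before that in 9.2 has medication administered on Day 1, Month 2 and Month 3, which conflicts with the daily bedtime regimen in 8.1.4. Those passages must be reconciled before the dose-time statement is relied on.

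**Scale.** SAP 9.1 tabulates subjects with any event, so one patient moves overall TEAE incidence by at most 1/n:
- 17 enrolled (SAP 3.1), all assumed to be in the Safety population: 1/17 = 5.9 percentage points.
- 30 completed, as planned: 1/30 = 3.3 percentage points.
- A patient with another TEAE moves it by 0, being counted already.

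The documents do not say how many Day 1 pre-dose events occurred.

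**The case against.** The best defence is that the date rule errs on the safe side. It can add TEAEs but cannot remove any, and it fits a SAP that works in dates for study day, exposure, prior medication and imputation. This stands as to direction. It does not justify placing one event in two categories that are reported separately.

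A reader might infer that procedure reactions will be reported as drug reactions. The documents do not support that. SAP 4.4.1 has relationship to study medication, artificial tears and study procedures rated separately, and SAP 9.1 tabulates all three. An event entered as a PTE has no drug-causality rating, so the date rule cannot by itself make it drug-related. Nor would correcting the rule clear procedure reactions from the TEAE tables. Fluorescein is used again at Months 1, 2 and 3, and dilation, tonometry and Schirmer at Month 3; reactions then follow the first dose and are TEAEs under the protocol too. What remains is the overall incidence and the double entry, for part of one day.

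A reader might also infer an undeclared departure from the protocol, since SAP section 10 does not list the date rule. The SAP states that it applies to protocol version 3.0, while the version available is 4.0. Whether 12.6 reads the same in 3.0 cannot be checked. The overlap inside SAP 4.4.1 does not depend on this.

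Finally, a dependable time for a first dose taken at home is not assured. Compliance is measured by container count, and no diary is described. That limits how well the fix will work, not whether the rule is wrong.

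**Conclusion.** The point holds. As written, SAP 4.4.1 gives a Day 1 pre-dose event two classifications, one of which contradicts protocol 12.6 and 10.2.1.1 in version 4.0. This rests on the first dose falling on the Day 1 date, as SAP 4.1.2 states.

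The consequence is modest. It touches safety tables only; the primary correlations are unaffected. The figure of 5.9 points is a ceiling for one patient, not an amount that every such event adds, and it carries the two conditions shown in the scale calculation. It would not be right to say that the tolerability results are distorted by any known amount. The change is still worth making, because the rule is explicit, misclassifies a foreseeable type of event, and is cheap to correct.

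**What to change.** Amend SAP 4.4.1 as follows.

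1. A TEAE is an event with onset after the first dose, by date and time, or a pre-dose event that worsens after the first dose. The worsening is recorded as a separate AE, as protocol 10.1.5 requires.
2. A Day 1 event with onset before the first dose is a PTE and is not counted as a TEAE unless it worsens.
3. A Day 1 event whose order relative to the first dose cannot be determined from the recorded times counts as a TEAE.
4. Each recorded event falls in one category only.
5. Any intended departure from protocol 12.6 is listed in SAP section 10.

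The cost is a few sentences and a date-time comparison in the programming. No new data item is needed if event and dose times were collected as protocol 10.2.1.2 and 9.2 specify; confirm that the first-dose time is actually in the database. The small downside is reliance on those times: where they are missing, some Day 1 events will default to TEAE.
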